Specific Aim 3: Describe the sociodemographic factors and healthcare utilization in enrolled subjects for the 12 months leading up to a surgical procedure for the lumbar spine. Identify factors that could account for differences in opioid medication, and any potential interaction effect between intervention, opioid use, and clinical outcomes following surgery.

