At the 1-month and 6-month time points they will be asked to fill out the additional clinical outcomes measures detailed below (ODI, PCS, PSQI, NPRS). These can be done in person with a visit to the clinic, over the telephone, or by email – depending on what they consented to. They will be reached out to daily until contact is made.

Assessment	Visit / Follow Up (F/U) Interval				
	12 months prior	Same Day	1 month	6 months	12 months after
Screening		X			
Informed Consent, discuss Plan, etc.		X			
Randomization		X			
Demographics, History & Physical		X			
Treatment (video education)		X			
Neck Disability Index (cervical surgery)		X	X	X	
Oswestry Disability Index (lumb surgery)		X	X	X	
The Opioid Risk Tool		X			
Pittsburg Sleep Quality Index		X	X	X	
Pain Catastrophizing Scale		X	X	X	
Medication use		X	X	X	
Numeric Pain Rating Scale		X	X	X	
Healthcare Utilization (MDR database)	X (entire 12 month period)				X (entire 12 month period)

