The goal of the MDR database will be to determine the medication utilization for each of these subjects, as well as any other healthcare related to low back pain sought in the 12-month period after treatment in this study. This data (type, location, number of clinic visits, types of specialty clinic visits, imaging, and associated medication) will allow us to determine the extent of low back pain related healthcare utilization for each subject.

- Recording of Extracted Data with Identifiers:

The data will be provided in a de-identified manner from PASBA. As they have done before with members of our team on prior project, they extract all the required data along with name, age and social security number in order to identify the correct subjects that were in our study. They will then assign a pseudo identification number and match that with the list of our subject identification numbers that we provide. Therefore, the final working set they provide us for analysis will not have any identifying PHI/PII associated with it. If additional follow-up is needed to clarify a healthcare utilization event in AHLTA, the research team can check the master subject record (stored on an encrypted government computer) in order to link the subject ID to SSN. Therefore, prior to analysis occurring, the identifiers will be eliminated. Confidentiality of protected health information will be maintained by the research staff at all times, however it should be minimal at this time. The final working database to be used in the data analysis will not include PHI information.

- Location of Extracted and Recorded Data:

The healthcare utilization data will be primarily extracted from the MDR database and through AHLTA. Even though the data is now de-identified, the extracted data will still be maintained in an encrypted, password protected file kept at the Physical Therapy Clinic, Brooke Army Medical Center.

- Nature of Identifying Data

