7.4.1 *Sample Size Estimation.* Collection of healthcare utilization will occur in 100% of the subjects as no follow-up is required, and therefore no opportunities to collect data from a follow-up visit will be lost. Therefore the sample size estimation is based on the secondary outcome variable of self-reported pain and function (OSW). Assuming at least 85% of patients complete the OSW at 6 months, enrollment of 60 subjects per group (total sample size 120 subjects) will provide at least 84% power to detect a difference of 12 points (2 X MCID) on the change in OSW to 26 weeks, assuming a standard deviation in the change in OSW of 16 points (treatment effect = 43.8% of one standard deviation). The MCID for both the OSW and NDI has been estimated at 6 points.⁵⁵ Previous work with patients with acute LBP indicate that these estimates of anticipated effect size and standard deviation are realistic,⁷⁸⁻⁸⁰ and would be consistent with detecting an effect that is at least slightly in excess of the threshold for seeing significant change. The NDI and OSW are similar in length and answer-type, and as we are expecting a higher number of lumbar patients, we will use the OSW to power this study.

Estimate Required Sample Size	101
Estimate Participant Drop Out / Withdrawal	19
Total Enrollment Requirement	120

Enrollment at Each Site	
--------------------------------	--

BAMC	120
------	-----

7.4.2 Primary (i.e., primary outcome variables) and secondary endpoints.

Primary Outcome Variable: Spinal pain healthcare utilization during the 1 year after enrollment understanding patients are likely still receiving care for their surgery at 6 months. This will include a comparison of imaging orders and types, specialty referrals, and medication use (pain and narcotics).

The self-reported outcome measures will also be taken at baseline, 1 month, and 6 months.

7.4.3 Data analysis.

All data will be analysed in IBM SPSS 21 (Chicago, IL). Descriptive statistics will be performed to describe the sociodemographic (age, sex, race, etc.) and health characteristics (disability, pain intensity, psychosocial factors, etc.) of the entire sample, and comparisons made between groups. Means and standard deviations will be computed for continuous data and frequency distributions will be analysed for categorical data.

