Specific Aim #1 will be evaluated by determining the RR (risk ratio) for opioid medication use during the 1 year following surgery between both groups. Utilization reports will be broken down into the 1st week (expected to be the highest), 1st month, and then from 2 through 1 year. We will also look at all healthcare utilization events between patients associated with lumbar ICD-9 codes (Appendix A) in those randomized to also view the educational video.

Comparison of self-report outcomes between groups at baseline and 6 months will be performed using a linear mixed-effects model, which is flexible in accommodating data assumed to be missing at random (Specific Aim #2). The time points will be baseline, 1 month, and 6 months for the measures collected from the patient (self-report questionnaires). Significance is set at 0.05 and 95% confidence intervals will be reported for all relevant data. Sensitivity analysis will be run adjusting for other demographic and/or prognostic variables (PCS, pain intensity, ESS, etc) that may affect the outcome.

Specific Aim #3 will be determined by comparing the variables between each group and introducing them as covariates into the linear mixed-effects model to see if the adjustment influences the differences between each group.

Point estimates with 95% Confidence Intervals will be reported.

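### Prior-year utilization is collected for every patient but never enters the comparison of 1-year utilization, so the primary outcome forgoes a near-costless gain in precision of unknown size

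*Combined protocol and SAP*

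**What the plan says.** - **Primary outcome (7.4.2).** The outcome is "Spinal pain healthcare utilization during the 1 year after enrollment". Its content is given as: "This will include a comparison of imaging orders and types, specialty referrals, and medication use (pain and narcotics".
- **What is extracted (7.3 schedule, 7.3.2).** The schedule row "Healthcare Utilization (MDR database") is marked for the full year before and the full year after. Section 7.3.2 lists the items drawn for the period after treatment: "type, location, number of clinic visits, types of specialty clinic visits, imaging, and associated medication". Section 7.4.1 expects complete data: "Collection of healthcare utilization will occur in 100% of the subjects as no follow-up is required".
- **Stated use of the prior year (section 3, Aim 3).** The aim is to describe "healthcare utilization in enrolled subjects for the 12 months leading up to a surgical procedure for the lumbar spine". It goes on to look for factors that might explain differences in opioid use, and for interactions.
- **Analysis (7.4.3).** Aim 1 is a risk ratio for opioid use, with no covariate named. Other utilization events will be looked at, with no model, effect measure or covariate. The linear mixed-effects model is defined for self-report outcomes at baseline, 1 month and 6 months. The Aim 3 variables are handled by "introducing them as covariates into the linear mixed-effects model to see if the adjustment influences the differences between each group". The sensitivity adjustment sits in the self-report paragraph, and its named examples do not include prior utilization.
- **Randomization (7.3).** Permuted blocks of two or four, with no stratification factor named.

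**The concern.** Patients awaiting spine surgery probably differ a good deal in how much spine care they use. If use before surgery predicts use after it, part of the spread in the 1-year counts is predictable. Left out of the model, that part stays in the error term of the primary comparison. With 60 patients per arm, and no stratification on prior use, it can widen the confidence interval noticeably.

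A baseline from the same database over a window of the same length is the natural covariate for removing it, and this trial already plans to obtain one. Because 7.4.3 is silent on the model, any adjustment would also have to be chosen later, possibly with the results in view.

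**Working it through.** **1. Can any planned model use the prior-year value for the primary outcome?** The only model in 7.4.3 that takes covariates has three questionnaire time points, the last at 6 months. A 12-month utilization total is not an outcome of that model. The Aim 1 risk ratio and the sentence on other utilization events name no covariate. So no planned analysis of utilization uses the prior year.

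**2. The plan's own power figure.** Section 7.4.1 states at least 84% power, but for the OSW. Using power = Φ(d × √(n/2) − 1.96), with n = 0.85 × 60 = 51 per arm and two-sided 0.05 (sidedness is assumed):
- 12 points with SD 16: d = 12/16 = 0.75; 0.75 × 5.050 − 1.96 = 1.83; power 96.6%.
- The stated 43.8% of an SD (7/16): 0.4375 × 5.050 − 1.96 = 0.25; power 59.8%.

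Neither gives 84%. The figure concerns another outcome, so nothing below depends on it. It serves only as an illustrative starting level.

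**3. Gain from adjustment.** Inputs: 60 per arm (7.4.1), utilization on all subjects (7.4.1), alpha 0.05 (7.4.3). The correlation ρ between prior-year and following-year use is assumed, because the documents give none. The variance ratio is 1 − ρ², the adjusted standardized effect is d/√(1 − ρ²), and the equivalent n per arm is 60/(1 − ρ²). By noncentral t, 84% unadjusted power at 60 per arm corresponds to d = 0.544.

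| ρ | 1 − ρ² | adjusted d | equivalent n per arm | power |
|---|---|---|---|---|
| 0 | 1.00 | 0.544 | 60 | 84.0% |
| 0.2 | 0.96 | 0.555 | 62.5 | 85.4% |
| 0.3 | 0.91 | 0.570 | 65.9 | 87.2% |
| 0.4 | 0.84 | 0.593 | 71.4 | 89.7% |
| 0.5 | 0.75 | 0.628 | 80 | 92.7% |
| 0.6 | 0.64 | 0.680 | 93.8 | 95.8% |
| 0.7 | 0.51 | 0.762 | 117.6 | 98.5% |

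The gain reaches 5 points at ρ of about 0.375. From 50% unadjusted power, ρ = 0.5 gives 61.9%. The lost degree of freedom is repaid once ρ exceeds about √(1/117) = 0.09.

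**4. Check with counts.** Overdispersed counts were simulated with 60 per arm and analysed by Poisson regression with robust standard errors, with and without log(1 + prior count). All rates are assumed.
- Mean parameter 6, log-normal SD 0.8, rate ratio 0.65, 600 trials per setting. At observed log-scale correlations of 0.15, 0.31, 0.46 and 0.60 the variance ratios were 0.99, 0.88, 0.79 and 0.61. Power rose from about 68–69% to 69%, 72%, 78% and 88%.
- Rate ratio 0.60, 800 trials, correlation about 0.54 at mean 8. Power rose from 69% to 82% at mean 8, from 60% to 68% at mean 2, and from 50% to 55% at mean 1. Sparse counts limit the correlation that can be attained.
- Under no effect (a similar simulation, mean parameter 8, 1,500 replicates), type I error was 5.2% unadjusted and 5.7% adjusted.

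**The case against.** The strongest reply has four parts.

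- **Aim 3 already provides for adjustment.** It does go beyond description, so a reader who infers that prior utilization is used only to describe the sample goes too far: section 3 also seeks explanatory factors, and 7.4.3 enters the Aim 3 variables as covariates. But they enter a model for self-report outcomes, as a check on whether the group difference moves. That recovers nothing for the utilization comparison.
- **The plan does not prescribe an unadjusted comparison.** This stands. A reader might infer that a crude comparison of totals was chosen, but for non-opioid utilization 7.4.3 specifies no analysis at all. The missing covariate is one part of that gap, and a model has to be named first.
- **The correlation may be low.** This also stands. Patients have had the condition for at least 6 months and are already scheduled for surgery (7.1.3), so the prior year probably contains the surgical work-up. The following year contains post-operative care, which 7.4.2 itself expects to continue at 6 months. Nor is it certain that the two windows measure the same thing. The schedule lists no components, the item list in 7.3.2 covers only the period after treatment, and 7.4.3 cites lumbar codes although 7.1.3 admits cervical patients.
- **It may be late to prespecify.** The April 2018 text in 7.1.6 says subject follow-up was complete, and section 13 plans the data request for November 2017 and completed analysis by May 2018. The documents do not say whether utilization had been compared by arm. The fix has to allow for either case.

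**Conclusion.** The point holds as a matter of precision. The trial collects a prior-year baseline for its primary outcome and plans no analysis that uses it there.

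A reader might infer that the primary comparison is biased, or that chance imbalance in prior use invalidates it. The documents do not support that: allocation is randomized, and the unadjusted comparison remains valid.

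Nor can any single gain be claimed. It is 1 to 3 points of power at ρ of 0.2 to 0.3, about 9 points at 0.5 and about 14 at 0.7, starting from an illustrative 84%. It is smaller for components with about one or two events per patient. Those figures assume two-sided testing, 60 per arm with complete data, and the stated ρ. The plan gives no rate, variance, correlation or power for utilization. The case for the change is that it costs almost nothing even if ρ proves low, and that it supplies a model these components now lack.

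**What to change.** Add to 7.4.3, in substance:

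> Each countable non-opioid component of the primary outcome (imaging orders, specialty referrals, non-opioid pain medication) will be compared between arms with a count regression, either negative binomial or Poisson with robust standard errors. The model will contain arm and log(1 + the patient's count of the same component in the 12 months before enrollment). The same code definitions will apply in both windows. The adjusted rate ratio with its 95% confidence interval will be reported, with the unadjusted ratio alongside.

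Choose one of the two model forms when the text is written. Four limits belong with it:
- Imaging types stay descriptive, because a count model does not address them.
- The Aim 1 opioid risk ratio is unchanged.
- The components are not each treated as a separate confirmatory primary test, since the plan has no multiplicity rule.
- The wording is fixed before utilization is compared by arm. If that comparison has already been made, the adjusted analysis is labelled as added later.

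The cost is a paragraph of text, agreement on code definitions for both windows, and one extra parameter per model with 120 patients. No new data or patient contact is needed, because the prior-year extraction is already scheduled. Prior utilization can still be described under Aim 3.

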1
2
3
Regional Health Command-Central (RHC-C)
Institutional Review Board

**HUMAN SUBJECTS RESEARCH
PROTOCOL APPLICATION – Part B**

4
5
6
7
CLINICAL TRIALS: NCT02674711
4 May 2018

1
2
1. **PROTOCOL TITLE:** The Effect of a Pain Medication Educational Approach before Spinal Surgery on 6-month Post-Operative Use of Opioid Medication: A Randomized Clinical Trial

1
2
3
4
2. **ABSTRACT**

5
6
7
Background: Opioid-based pain medication use and prescription has increased dramatically in the last two decades, leading to high rates of overdose and utilization for patients with chronic non-cancer pain, despite lack of evidence to support its use. Very little research has looked at educational strategies to help address this problem.

8
9
Design: Randomized clinical trial

0
1
2
3
4
Methods: Subjects will be recruited from the pool of patients coming in for the pre-operative appointment prior to spine surgery. Patients that consent and enroll will be randomized to receive either a brief educational video at this appointment or usual care. Patients will be followed after surgery weekly for the first month, and then again at 6 months to determine their self reported opioid medication utilization patterns. Pain medication prescription and healthcare utilization will also be abstracted from the MDR healthcare database.

5
6
7
Summary: The results from this study will help inform and develop best practice for managing patients taking opioid medication for surgical pain.

8
9
3. **OBJECTIVES/SPECIFIC AIMS/RESEARCH QUESTIONS.**

0
1
2
3
4
This study is a continued project in a line of research aimed at improving the quality of spinal pain management. The purpose of this project is to assess the impact of an educational tool that addresses the latest evidence regarding the use of opioid medication in a patient-centric fashion. We will assess the impact this shared-decision making educational tool has on 12 month health care utilization post operatively and the self reported use of narcotic pain medication usage for the 6 months following lumbar spine surgery.

5
6
7
Specific Aim 1: Evaluate the differences in opioid medication use for the 12-month period after surgery in subjects that received the education prior to surgery compared to those that received usual care education.

8
9
Specific Aim 2: Compare the changes in self-reported outcome measures (pain, disability, and sleep) between groups over the 6-month period after surgery.

0
1
2
3
4

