| available evidence³⁸. The observed variation in geographic differences in surgical rates and postoperative
| recommendations may adversely affect the clinical outcomes associated with lumbar spine surgery. Previous
| research has demonstrated that the clinical outcomes following lumbar disc surgery are suboptimal with many
| patients experiencing recalcitrant pain, disability and reduced quality of life³⁹⁻⁴³. Prolonged opiate use after
| cervical surgery is also a problem.⁷⁵ Indeed, unsuccessful spine surgery has been described as a major health-
| care problem⁴⁴.

) Opioid-based drugs are often used to help manage pain after spinal surgery.^{19,45,46} However, it is also used often
| to manage spine pain in general, even prior to surgical interventions.³³ This is despite a recent systematic review
| that found only a very modest effect, and that was in the short term.⁴⁷ The outcomes for chronic pain, greater
| than 4 months, were not available.⁴⁷ Even the Cochrane collaboration back group has stated that "the benefit of
| opioids in clinical practice for the long-term management of chronic [low back pain] remains questionable."⁴⁸
| Other studies show that when patients receive opioids for treatment of non-cancer pain, high levels of pain
| remain persistent and their quality of life decreases.⁴⁹

7 Ironically, pre-operative use of opioid medications is actually a predictor of worse outcome after spine
| surgery.⁵⁰ Another study found that 1/3 of patients were still using opioid pain medication one year **after** their
| spine surgery.⁵¹

2 *Opioid Abuse in the Military*

) Abuse of opioid pain medication may be even higher in the military.^{18,20,21} The U.S. Military faces a post-war
| chronic pain epidemic. Chronic pain after musculoskeletal injury is the leading cause of medical discharge and
| related to a growing rate of opioid addiction. Traditional medical management has failed to correct this chronic
| pain epidemic.

3 *Education Initiatives/Intervention*

) Most clinical guidelines recommend an informed decision process between the provider and the patient. Deyo
| and colleagues argue that patients need to be better social support and honest preparation to deal with their
| circumstances: "Patients need realistic expectations despite product marketing, media reports, and medical
| rhetoric that promise a pain-free life."³³

) The American Pain Society and the American College of Physicians has provided guidance on prescription of

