7.2.1 N/A

7.2.2 N/A

7.3. Study Procedures/Research Interventions.

After consenting, meeting inclusion criteria, and enrollment, all participants will complete several standard self-report questionnaires related to medical history, social demographic, and psychosocial variables that are related to low back pain, and often used in clinics as standard care in managing patients with spinal pain. Patients undergoing lumbar spine surgery will fill out the OSW and patients undergoing cervical spine surgery will fill out the NDI. They will then be randomized to either receive the education, or only usual care (which is the typical information the surgeon provides the patient verbally). All patients will receive the usual care education from their surgeon.

Randomization:

Subjects will then be randomized into one of two arms (Group I = Educational Video, Group II= Usual Care Education). The method of group assignment will be sequentially numbered opaque sealed envelopes (SNOSE). To minimize the risk of predicting the treatment assignment of the next eligible patient, randomization will be performed in permuted blocks of two or four with random variation of the blocking number.

Education Group:

The educational video chosen for this education is one created by [name], a physician and associate professor of Family and Community Medicine at the University of Toronto, CA, with a strong research focus on patient engagement. He runs the Health Design Lab which has produced several dozen patient engagement videos on a variety of public health topics. They are well-vetted, strongly based on evidence, and have been profiled by organizations such as the Journal of the American Medical Association (JAMA).

The video we are choosing for the educational intervention is titled: ***Best Advice for People Taking Opioid Medication*** and is available at the URL: <http://www.youtube.com/watch?v=7Na2m7lx-hU>

The content of the education focus on providing a historical perspective for opioid prescription from the time when the risk of dependence was highly underestimated. The video discusses the current evidence for the effect of opioid medications in non-cancer non-acute pain. It also discusses some of the dangers of long-term opioid usage. The video is 11 and ½ minutes long.

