Pittsburg Sleep Quality Index (PSQI) The Pittsburg Sleep Quality Index (PSQI) is a self-rated questionnaire which assesses sleep quality and disturbances. Clinical properties provide utility in both psychiatric clinical practices and research activities. Seven “component” scores including: subjective sleep quality, sleep latency, sleep duration, habitual sleep efficiency, sleep disturbances, use of sleep medication, and daytime dysfunction are generated from 19 individual items.⁶³ Sleep quality may have a significant role in affecting outcomes of patients with low back pain as several studies have shown correlation between chronic back pain and quality of sleep.^{70, 71}

Fear Avoidance Belief Questionnaire (FABQ): The⁷² will be used to measure patients’ beliefs about how physical activity and work may affect their pain and perceived risk for re-injury. The FABQ contains two subscales; a 7-item work subscale (FABQW), and 4-item physical activity subscale (FABQPA). Test-retest reliability of the FABQ subscales is high,^{72,73} and validity is supported by associations with disability and work loss in patients with acute and chronic LBP.^{74,75} Heightened fear-avoidance beliefs have been shown to be a risk factor for the development of chronic LBP following an acute episode.^{62,76} Other research suggests it may be appropriate for other body regions, specifically evaluating its use in lower extremity injuries within a physical therapy setting.⁷⁷

Healthcare Utilization

Finally, healthcare utilization data will be collected from the MHS Data Repository (MDR) database and will be confirmed via AHLTA. Healthcare utilization data will be used to determine any opioid medication use along with any subsequent medical utilization related to low back or neck pain. In order to collect this information a DUA will be completed between the researcher team and Patient Administration Systems and Biostatistics Activity (PASBA) and the Tricare Management Agency (TMA). Both of these agencies require a signed completed IRB protocol prior to submitting the DUA. However, this should not impact the timing of this study; as the data pull will be completed no sooner than December 2015. This will provide more than enough time to complete the DUA with both agencies and submit the signed DUA to the BAMC IRB prior to performing this analysis. Details for the determining healthcare utilization are outlined below:

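### Aim 1's one-year risk ratio does not define an opioid user and is not tied to the later period; if it counts any use and early use is high, it hardly responds to later use

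*Combined protocol and SAP*

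**What the plan says.** Section 3 states Aim 1 as "Evaluate the differences in opioid medication use for the 12-month period after surgery". Section 7.4.3 evaluates it by "determining the RR (risk ratio) for opioid medication use during the 1 year following surgery between both groups". The full-year window therefore follows from the aim.

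The next sentence of 7.4.3 reads "Utilization reports will be broken down into the 1st week (expected to be the highest), 1st month, and then from 2 through 1 year". The last period has no unit; month 2 is the natural reading. The sentence concerns utilization reports and does not say that a risk ratio is computed in each period.

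No section gives a rule for a user. The nearest text, in 7.3.2 (Healthcare Utilization), says the extract will be "used to determine any opioid medication use along with any subsequent medical utilization related to low back or neck pain", which describes the purpose of the data. Section 7.4.2 lists medication use within the primary outcome without a metric. Opioid intake is also self-reported: weekly in month 1 (7.3), with medication use scheduled at baseline, 1 month and 6 months. No text says which source feeds the risk ratio.

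The time origin also differs: 7.4.2 counts the year from enrollment, 7.4.3 from surgery.

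No covariate is named for the risk ratio. The sentence "Sensitivity analysis will be run adjusting for other demographic and/or prognostic variables (PCS, pain intensity, ESS, etc) that may affect the outcome" stands in the self-report paragraph and does not name pre-operative opioid use. MDR utilization is collected for the 12 months before surgery, and section 5 says "pre-operative use of opioid medications is actually a predictor of worse outcome after spine" surgery.

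**The concern.** A risk ratio needs a yes/no rule for each patient. Without one, two analysts could follow this plan and report different Aim 1 results.

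The most natural reading of an undefined risk is any use in the window. On that reading, one fill shortly after surgery makes a patient a user for the whole year. Where most patients fill a prescription early, nearly everyone in both arms is a user, and later differences have little room to show.

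Later use is a large part of the trial's motivation. Of the video, 7.3 says "It also discusses some of the dangers of long-term opioid usage", and section 5 reports: "Another study found that 1/3 of patients were still using opioid pain medication one year" after spine surgery. A full-year ratio near 1 could be misread as no effect on persistent use.

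**Working it through.** **The plan's own figure.** There is none for this comparison. The only power statement (7.4.1, at least 84%) concerns the change in OSW, and nothing below depends on it.

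**Inputs from the documents.** 60 per arm and complete utilization data (7.4.1); significance level 0.05 (7.4.3), taken as two-sided; one third still using at one year, from a study cited in section 5. That third is a point figure, not a design assumption of this trial. Cumulative use over months 2 to 12 would usually be at least as high, so values up to 60% are also shown.

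**Assumptions not in the documents.** Use means any use. Early use *e* is equal in both arms and independent of later use *L*. The video halves *L*.

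**Formula.** Full-year risk = e + (1 − e) × L under usual care, and e + (1 − e) × L/2 with the video. The risk ratio (RR) is video over usual care. Power is exact, for the pooled two-proportion z-test.

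Example, e = 0.90 and L = 1/3: usual care 0.90 + 0.10 × 1/3 = 0.933; video 0.90 + 0.10 × 1/6 = 0.917; RR = 0.917/0.933 = 0.982.

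| Early use e | Full-year RR, L = 1/3 | Power | Full-year RR, L = 0.60 | Power |
|---|---|---|---|---|
| 0.50 | 0.875 | 16% | 0.813 | 46% |
| 0.70 | 0.938 | 10% | 0.898 | 26% |
| 0.80 | 0.962 | 8% | 0.935 | 18% |
| 0.90 | 0.982 | 6% | 0.969 | 10% |
| 0.95 | 0.991 | 5% | 0.985 | 5% |
| 0.98 | 0.997 | 1% | 0.994 | 1% |
| Later window only | 0.50 | 57% | 0.50 | 92% |

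With L = 0.50, later-window power is 82%, against at most 13% for the full year when e is 0.80 or more.

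The 1% entries should not be read as dilution alone. At e = 0.98 and L = 1/3 the test's actual size is only 0.8%, so the low figure mostly reflects a conservative test near the boundary. The RR column is the better guide.

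**Bounds.** With equal e, the video risk is at least e and the usual-care risk at most 1, so the full-year RR cannot fall below e. If every later user was also an early user, it is exactly 1.

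**Sample size for 80% power.** n = [1.96√(2p̄(1 − p̄)) + 0.842√(p₀(1 − p₀) + p₁(1 − p₁))]² / (p₀ − p₁)². For 1/3 vs 1/6 this gives 105 per arm. For the same change seen through the full-year risk at e = 0.90 (0.933 vs 0.917) it gives 3,920.

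**If early use also falls.** With early use of 80% to 98% under usual care, 5 to 10 points lower with the video, and L = 1/3 or 0.60, the full-year RR is 0.86 to 0.95 and power 19% to 57%.

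**Adjustment for pre-operative use.** Simulated modified Poisson fits of the later-window RR (6,000 replicates per scenario) changed power by −0.6 to +7.4 points. The negative value came from a covariate unrelated to the outcome.

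**The case against.** The strongest reply is that the later period is already in the plan. It stands directly after the risk-ratio sentence, and 7.4.3 promises point estimates with 95% confidence intervals. A reader would probably see later use by arm. That much stands: one might infer that the plan ignores later use, and the text does not support that. The gap is narrower. No ratio is tied to that period, and nothing says which period answers the question about later use.

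Second, the dilution is conditional. One might infer that the full-year ratio is bound to sit near 1. The documents give neither an any-use rule nor an early-use rate. High early use is plausible: section 5 says opioids are often used after spinal surgery, 7.1.3 excludes patients who cannot take them, and week 1 is expected to be the highest. At 50% to 70% early use, however, the ratio moves visibly, and an effect on early use would move it too.

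Third, one might infer that leaving out pre-operative use biases the comparison. It does not: allocation is randomized, and the unadjusted ratio is valid. Only a little precision is at stake.

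Finally, an any-fill rule for months 2 to 12 would repeat the problem on a smaller scale, since one refill early in month 2 makes a patient a later user. This is a fair criticism and calls for a stricter sensitivity rule.

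**Conclusion.** The concern holds in a limited form and should be fixed. The textual gap needs no assumption: the user rule, data source, time origin, unit of the last period and periods for which a ratio is computed are all unstated or unreconciled. The consequence does need assumptions. With an any-use rule, equal early use of 80% or more, and later use halved from 1/3 to 1/6, the full-year ratio is about 0.96 to 1.00 against 0.50 in the later window. At early use of 50% to 70% it is 0.88 to 0.94 for later use of 1/3, and as low as 0.81 for later use of 60%. Confidence is medium, because the early-use level is unknown. A full-year ratio near 1 would not, on these figures, be evidence of no effect on later use.

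**What to change.** Before utilization data are seen by arm:

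1. State that the risk ratio uses MDR opioid fills; scheduled self-report stops at 6 months and cannot cover the year. Define a user, for example at least one opioid fill in the period. Add a sensitivity analysis with a stricter rule, such as two or more fills or a fill in the second half of the year, so that one early refill does not define later use.
2. Write the last period as month 2 through month 12. Count from one stated origin, reconciling 7.4.2 with 7.4.3. Compute the ratio with 95% CI for week 1, month 1, months 2 to 12 and the full year.
3. Name the months 2 to 12 ratio in advance as the comparison that answers the question about later use. Keep the full-year ratio for Aim 1 as stated, and do not read a value near 1 as no effect on later use.
4. Adjust for any opioid fill in the 12 pre-operative months by modified Poisson regression with robust standard errors, with the unadjusted ratio beside it. If the model does not converge, report the unadjusted ratio.

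**Cost.** SAP wording and one regression on data already in the extract. Fills must be kept by week from the chosen origin. That is finer than 7.3.2, which codes the initial appointment in weeks and repeat visits as a range. Several period ratios add comparisons, hence the need to name one. Precision stays limited: 10/60 vs 20/60 later users gives 0.50 (95% CI 0.26 to 0.98).

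The change is late. Section 13.0 plans the data request for November 2017, and the April 2018 amendment in 7.1.6 says follow-up with subjects was complete. With enrollment planned to end in May 2017, 12-month data would run to May 2018, but a 6-month extract may already have been seen. Record the date of the change and whether arm-level data had been seen. If they had, keep the planned ratio and label the others post hoc.
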